## Appendix 1. Abbreviations

This following is a list of abbreviations that may be used in the protocol.

Abbreviation	Term
AE	adverse event
AHD	antecedent haematologic disease
ALT	alanine aminotransferase
ALL	Acute Lymphoblastic Leukemia
AML	Acute Myelogenous Leukemia
ANC	absolute neutrophil count
APL	Acute Promyelocytic Leukemia
Ara-C	Cytarabine
ASCO	American Society for Clinical Oncology
CCI	
AST	aspartate aminotransferase
ATRA	all-trans retinoic acid
AUC	area under the curve
AUC inf	area under the plasma concentration-time profile from time 0 to infinity
AZA	azacitidine
CCI	
BCR-ABL1	BCR-ABL breakpoint cluster region-Abelson 1
BID	twice a day
BM	bone marrow
BSA	body surface area
BST	best supportive therapy
Ca	calcium
C avg ss	steady state average concentration
CALGB	Cancer and Leukemia Group B
CBC	complete blood count
C#D#	Cycle # Day #
CD	cluster of differentiation
CDF	cumulative distribution functions
CI	confidence interval
CID	clinically important difference
CK	creatinine kinase
C max	maximum plasma concentration
CMH	Cochran Mantel Haenszel
CMML	Chronic myelomonocytic leukemia
CNS	central nervous system
CR	complete remission
CRh	complete remission with partial hematologic recovery
CRi	complete remission with incomplete hematologic recovery

Abbreviation	Term
CR MRD-neg	complete remission with negative minimal residual disease
CRF	case report form
CSA	clinical study agreement
CT	clinical trial
CTC	common terminology criteria
CTCAE	common terminology criteria for adverse events
C trough	plasma trough concentration
CV	coefficient of variation
DDI	Drug-drug interaction
DILI	drug-induced liver injury
DLT	dose limiting toxicity
CCI	
DoR	duration of response
DoRi	duration of response (response is defined as CRi or better)
DoRh	duration of response (response is defined as CRh or better)
DU	dispensable unit
EC	ethics committee
ECG	electrocardiogram
ECHO	echocardiogram
ECOG	Eastern Cooperative Oncology Group
E-DMC	external data monitoring committee
EDP	exposure during pregnancy
EFS	event-free survival
ELN	European Leukemia Net
EQ-VAS	EQ-5D visual analogue scale
EU	European Union
EudraCT	European Clinical Trials Database
EQ-5D-5L	EuroQol 5-Dimension questionnaire 5-Level version
FAS	full analysis set
FDA	Food and Drug Administration
FIP	first-in-participant
FLT3-ITD	fms-like tyrosine kinase internal tandem duplication
FSH	follicle-stimulating hormone
fu	fraction unbound
GCP	good clinical practice
G-CSF	granulocyte-colony stimulating factor
GGT	gamma-glutamyl transferase
GLI	glioma-associated oncogene homolog 1
GLP	good laboratory practice
GM-CSF	granulocyte-macrophage colony stimulating factor
GVHD	graft-versus-host disease
hCG	human chorionic gonadotropin

Abbreviation	Term
HDPE	high density polyethylene
HGRAC	Human Genetics Resources Administration of China
Hh	hedgehog
HIDAC	high dose Ara-C
HIV	human immunodeficiency virus
HR	Hazard ratio
HRQL	health-related quality of life
HRT	hormone replacement therapy
HSCT	hematopoietic stem cell transplant
IB	Investigator Brochure
ICH	International Conference on Harmonisation
ID	identification
IIR	investigator-initiated research
IND	investigational new drug application
INR	international normalized ratio
IP	investigational product
IRB	institutional review board
IRT	interactive response technology
IUD	intrauterine device
IV	intravenous
IVR	interactive Voice Response
IWR	interactive web response
JAK	janus kinase
K	potassium
CCI	
LDAC	low-dose cytarabine
LFT	liver function test
LIC	lead-in cohort
LSC	leukemia stem cells
LSLV	last subject last visit
LVEF	left ventricular ejection fraction
MD	medical doctor
MDASI	MD Anderson Symptom Inventory
MDR-1	multi-drug resistance-1
MDS	myelodysplastic syndrome
MedDRA	Medical Dictionary for Regulatory Activities
MF	myelofibrosis
Mg	magnesium
MLFS	morphologic leukemia-free state
MnB	meningitidis serogroup B
MRD	minimal residual disease
MTD	maximum tolerated dose
MUGA	multigated acquisition scan

Abbreviation	Term
mCR	marrow complete remission
mOS	median overall survival
n	number
NCI	National Cancer Institute
NIH	National Institutes of Health
N/A	not applicable
NOAEL	no observed adverse effect level
NPM1	nucleophosmin 1
NRS	numeric rating scale
OS	overall survival
PCD	primary completion date
PD	progressive disease
PDx	pharmacodynamics(s)
PE	physical examination
PEG	pegylated
PGIC	Patient Global Impression of Change
PGIS	Patient Global Impression of Symptoms
P-gp	p-glycoprotein
PGx	pharmacogenomics(s)
PH	potential of hydrogen
PK	pharmacokinetic
PML-RARA	Promyelocytic leukemia – retinoic acid receptor alpha
PO	by mouth, orally
PR	partial remission
PRO	patient reported outcomes
CCI	
PT	prothrombin time
PTCH	patched
QALY	quality-adjusted life years
QD	once a day
QTc	QT interval corrected for rate
QTcF	QT interval corrected by the Fridericia Correction Formula
R ac	accumulation ratio
RMST	restricted mean survival time
RNA	ribonucleic acid
ROW	rest of world
RP2D	recommended Phase 2 dose
SAE	serious adverse event
SAP	statistical analysis plan
SC	subcutaneous
SCT	stem cell transplant
SD	stable disease

Abbreviation	Term
SMO	smoothened
SoA	schedule of activities
SOP	standard operating procedure
SPC	summary of product characteristics
SRSD	single reference safety document
Stdev	standard deviation
SUSAR	suspected unexpected serious adverse reaction
TBili	total bilirubin
TdP	torsades de pointes
TEAE	treatment emergent adverse events
TESAE	treatment emergent serious adverse events
CCI	
TF	treatment failure
TKI	tyrosine kinase inhibitor
T max	time to maximum plasma concentration
TTR	time to response
TTR i	time to response (response is defined as CR i or better)
TTR h	time to response (response is defined as CR h or better)
U/A	urinalysis
ULN	upper limit of normal
US	United States
UVB	ultraviolet B light
V z /F	Apparent volume of distribution
WHO	World Health Organization

## Appendix 2. 2016 WHO Classification of Myeloid Neoplasms and Acute Leukemia

### Myeloproliferative neoplasms (MPN)

Chronic myeloid leukemia (CML), *BCR-ABL1*+

Chronic neutrophilic leukemia (CNL)

Polycythemia vera (PV)

Primary myelofibrosis (PMF)

PMF, prefibrotic/early stage

PMF, overt fibrotic stage

Essential thrombocythemia (ET)

Chronic eosinophilic leukemia, not otherwise specified (NOS)

MPN, unclassifiable

### Mastocytosis

### Myeloid/lymphoid neoplasms with eosinophilia and rearrangement of *PDGFRA*, *PDGFRB*, or *FGFR1*, or with *PCM1-JAK2*

Myeloid/lymphoid neoplasms with *PDGFRA* rearrangement

Myeloid/lymphoid neoplasms with *PDGFRB* rearrangement

Myeloid/lymphoid neoplasms with *FGFR1* rearrangement

*Provisional entity: Myeloid/lymphoid neoplasms with PCM1-JAK2*

### Myelodysplastic/myeloproliferative neoplasms (MDS/MPN)

Chronic myelomonocytic leukemia (CMML)

Atypical chronic myeloid leukemia (aCML), *BCR-ABL1*

Juvenile myelomonocytic leukemia (JMML)

MDS/MPN with ring sideroblasts and thrombocytosis (MDS/MPN-RS-T)

MDS/MPN, unclassifiable

### Myelodysplastic syndromes (MDS)

MDS with single lineage dysplasia

MDS with ring sideroblasts (MDS-RS)

MDS-RS and single lineage dysplasia

MDS-RS and multilineage dysplasia

MDS with multilineage dysplasia

MDS with excess blasts

MDS with isolated del(5q)

MDS, unclassifiable

*Provisional entity: Refractory cytopenia of childhood*

Myeloid neoplasms with germ line predisposition

**Acute myeloid leukemia (AML) and related neoplasms**

AML with recurrent genetic abnormalities

AML with t(8;21)(q22;q22.1);*RUNX1-RUNX1T1*

AML with inv(16)(p13.1q22) or t(16;16)(p13.1;q22);*CBFB-MYH11*

APL with *PML-RARA*

AML with t(9;11)(p21.3;q23.3);*MLL T3-KMT2A*

AML with t(6;9)(p23;q34.1);*DEK-NUP214*

AML with inv(3)(q21.3q26.2) or t(3;3)(q21.3;q26.2); *GATA2, MECOM*

AML (megakaryoblastic) with t(1;22)(p13.3;q13.3);*RBM15-MKL1*

*Provisional entity: AML with BCR-ABL1*

AML with mutated *NPM1*

AML with biallelic mutations of *CEBPA*

*Provisional entity: AML with mutated RUNX1*

AML with myelodysplasia-related changes

Therapy-related myeloid neoplasms

AML, NOS

AML with minimal differentiation

AML without maturation

AML with maturation

Acute myelomonocytic leukemia

Acute monoblastic/monocytic leukemia

Pure erythroid leukemia

Acute megakaryoblastic leukemia

Acute basophilic leukemia

Acute panmyelosis with myelofibrosis

Myeloid sarcoma

Myeloid proliferations related to Down syndrome

Transient abnormal myelopoiesis (TAM)

Myeloid leukemia associated with Down syndrome

**Blastic plasmacytoid dendritic cell neoplasm**

**Acute leukemias of ambiguous lineage**

Acute undifferentiated leukemia

Mixed phenotype acute leukemia (MPAL) with t(9;22)(q34.1;q11.2); *BCR-ABL1*

MPAL with t(v;11q23.3); *KMT2A* rearranged

MPAL, B/myeloid, NOS

MPAL, T/myeloid, NOS

**B-lymphoblastic leukemia/lymphoma**

B-lymphoblastic leukemia/lymphoma, NOS

B-lymphoblastic leukemia/lymphoma with recurrent genetic abnormalities

B-lymphoblastic leukemia/lymphoma with t(9;22)(q34.1;q11.2); *BCR-ABL1*

B-lymphoblastic leukemia/lymphoma with t(v;11q23.3); *KMT2A* rearranged

B-lymphoblastic leukemia/lymphoma with t(12;21)(p13.2;q22.1); *ETV6-RUNX1*

B-lymphoblastic leukemia/lymphoma with hyperdiploidy

B-lymphoblastic leukemia/lymphoma with hypodiploidy

B-lymphoblastic leukemia/lymphoma with t(5;14)(q31.1;q32.3) *IL3-IGH*

B-lymphoblastic leukemia/lymphoma with t(1;19)(q23;p13.3); *TCF3-PBX1*

*Provisional entity: B-lymphoblastic leukemia/lymphoma, BCR-ABL1–like*

*Provisional entity: B-lymphoblastic leukemia/lymphoma with iAMP21*

**T-lymphoblastic leukemia/lymphoma**

*Provisional entity: Early T-cell precursor lymphoblastic leukemia*

*Provisional entity: Natural killer (NK) cell lymphoblastic leukemia/lymphoma*

---

### **Appendix 3. Eastern Cooperative Oncology Group Performance Status**

#### **ECOG PERFORMANCE STATUS\***

Grade	ECOG
0	Fully active, able to carry on all pre-disease performance without restriction
1	Restricted in physically strenuous activity but ambulatory and able to carry out work of a light or sedentary nature, eg, light house work, office work
2	Ambulatory and capable of all selfcare but unable to carry out any work activities. Up and about more than 50% of waking hours
3	Capable of only limited selfcare, confined to bed or chair more than 50% of waking hours
4	Completely disabled. Cannot carry on any selfcare. Totally confined to bed or chair
5	Dead

#### Appendix 4. Summary of Response Criteria and Progression Definitions for AML Treated with Intensive and Non-Intensive Chemotherapy used in BRIGHT AML1019

Response Criteria 	Minimal residual disease  (per central lab report only)	Peripheral Blood			Bone Marrow Blasts (%)	Other
		Neutrophils	Platelets	Peripheral Blasts (%)		
Treatment Response						
Complete Remission without minimal residual disease (CRM RD-)	MRD Negative	$\geq 1 \times 10^9 /L$ ( $\geq 1000 \mu L$ )	$\geq 100 \times 10^9 /L$ ( $\geq 100\ 000 \mu L$ )	0	<5	
Complete Remission (CR)	MRD positive or unknown	$\geq 1 \times 10^9 /L$ ( $\geq 1000 \mu L$ )	$\geq 100 \times 10^9 /L$ ( $\geq 100\ 000 \mu L$ )	0	<5	
 
Absence of extramedullary disease.
 
Absence of blasts with Auer rods.
 

Complete Remission with partial hematologic recovery (CRh)   APPLIES ONLY FOR THE NON-INTENSIVE STUDY	MRD positive or unknown	$\geq 0.5 \times 10^9 /L$ ( $500 \mu L$ )	$\geq 50 \times 10^9 /L$ ( $\geq 50\ 000 \mu L$ )	0	<5	
 
Assess in non-intensive chemotherapy study only, not qualifying for CR, ie, both neutrophil <math>\geq 0.5 \times 10^9 /L</math> and platelets <math>\geq 50 \times 10^9 /L</math> must be met, but does not satisfy both Neutrophils <math>\geq 1 \times 10^9 /L</math> and Platelets <math>\geq 100 \times 10^9 /L</math> at the same time.
 
Absence of extramedullary disease.
 
Absence of blasts with Auer rods.
 

Complete Remission with incomplete hematologic recovery (CRi)	MRD positive or unknown	$< 1 \times 10^9 /L$ ( $< 1000 \mu L$ )	$< 100 \times 10^9 /L$ ( $< 100\ 000 \mu L$ )	0	<5	
 
Not qualifying for CR or CRh (if applicable), ie,
 
For intensive chemotherapy study: either neutropenia (<math>< 1 \times 10^9 /L</math>) or platelets (<math>< 100 \times 10^9 /L</math>) must be met.
 
For non-intensive chemotherapy study, either neutrophil <math>< 0.5 \times 10^9 /L</math> or platelets <math>< 50 \times 10^9 /L</math> must be met.
 
Absence of extramedullary disease.
 
Absence of blasts with Auer rods.
 

Morphologic leukemia-free state (MLFS)	MRD positive or unknown				< 5	
 
Absence of extramedullary disease.
 
Absence of blasts with Auer rods.
 
No hematologic recovery required; marrow should not be aplastic; at least 200 cells enumerated or cellularity <math>\geq 10\%</math>.
 

Partial Remission	MRD	$\geq 1 \times 10^9 /L$	$\geq 100 \times 10^9 /L$	0	Decrease to	

(PR)	positive or unknown	(≥1000μL)	(<100 000μL)	5 – 25% AND Decrease of pre treatment bone marrow blast percentage by at least 50%.
Response criteria for clinical trials				
Stable Disease (SD)	
 
Absence of CRMRD-, CR, CRh (if applicable), CRi, PR, MLFS, and criteria for PD not met.
 
Period of stable disease should be at least 3 months in the non-intensive only. The 3 month criteria does not apply to the intensive study.
 
			
Progressive Disease (PD)	
 
Evidence for an increase in bone marrow blast percentage and/or increase of absolute blast counts in blood:
 
>50% increase over baseline (a minimum 15% point increase in cases with <30% blasts at baseline); or persistent marrow blast percentage of >70% over at least 3 months; without at least a 100% improvement in ANC to an absolute level (>0.5x10^9/L [500/μL], and/or platelet count to >50x10^9/L [50 000/μL] non-transfused); OR
 
>50% increase in peripheral blasts (WBC x %blasts) to >25x10^9/L (>25 000/μL) OR New extramedullary disease.
 
			
Indeterminate	A response that does not fit the criteria for SD or PD. For example, when peripheral blood blast count assessed and no bone marrow assessment, or when a technical issue prevents the ability to make a response assessment (ie dry tap or insufficient sample), or when an SD is not maintained for 3 months in the non-intensive study.			
Other Responses referenced in ELN 2017				
Relapse				
Hematologic relapse (after CRMRD-, CR, CRi)	Reappearance of blasts in peripheral blood; OR ≥5% bone marrow blasts; OR Development of extramedullary disease.			
Molecular Relapse (after CRMRD-)	Reoccurrence of MRD positive status.			
Treatment Failure				
Primary refractory disease	
For Intensive study: No CR or CRi after 2 courses of induction treatment; excluding patients with death in aplasia or death due to indeterminate cause.
 
For Non-Intensive study: failure to achieve CR or CRh following up to 6 cycles of study treatment, excluding patients with death in aplasia or death due to indeterminate cause.
			
Death in aplasia	Deaths occurring ≥7 days following completion of initial treatment while cytopenic; with an aplastic or hypoplastic bone marrow obtained within 7 days of death, without evidence of persistent leukemia.			
Death from indeterminate cause	Deaths occurring before completion of therapy, or <7 days following its completion or deaths occurring ≥7 days following completion of initial therapy with no blasts in the blood, but no bone marrow examination available.			

PF-04449913

B1371019

Final Protocol Amendment 5, 12 April 2019

1. This study uses modified 2017 ELN recommendations. The definitions used in this study are shown in this table. Original ELN recommendations are found in: Dohner H, Estey E, Grimwade D, et.al. Diagnosis and management of AML in adults: 2017 ELN recommendations from an international expert panel. Blood. 2017; 129 (4): 424-447.
2. CRh is not part of the 2017 ELN recommendations, but is a required assessment for the non-intensive chemotherapy study.
3. 2017 ELN recommendations are found in: Dohner H, Estey E, Grimwade D, et.al. Diagnosis and management of AML in adults: 2017 ELN recommendations from an international expert panel. Blood. 2017; 129 (4):424-447.

CCI

CCI

CCI

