## **7.2. Efficacy Assessments**

### **7.2.1. AML Response Criteria**

Disease response, measured from baseline through the End of Treatment will be evaluated using a modified version of the European LeukemiaNet (ELN) recommendations for diagnosis and management of AML in adults ([Appendix 4](#)). ELN response assessments include evaluation of bone marrow, peripheral blood neutrophils, platelets, and blast %, assessment for EMD, and results from central lab MRD assessment. Every subject must have an Investigator determined Response Assessment documented per [Appendix 4](#) or response should be marked as indeterminate if the evaluation does not meet a specific ELN response criterion.

All subject files and bone marrow assessment slides/samples must be available for source verification.

CR with partial hematologic recovery (CRh) will be assessed for the Non-intensive chemotherapy study. CRh is defined as ANC  $>0.5 \times 10^9/L$  and platelets  $>50 \times 10^9/L$  without qualifying for CR.

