### **7.2.3. Bone Marrow Assessments**

Please see the [Schedule of Activities](#) for specific assessment time points for BM biopsy and/or aspirate collection. Bone marrow samples should be prepared according to the study Laboratory Manual. Results of all bone marrow evaluations performed during the study participation will be reported in the CRF.

The importance of timely and complete disease assessments (including BM assessments) at screening and during the study cannot be understated. Failure to perform any of the required disease assessments will result in the inability to determine disease status for that time point and have the potential to weaken the conclusions of this study.

CCI [REDACTED]

[REDACTED]

[REDACTED]

[REDACTED]

The two samples that are collected for MRD analysis, the bone marrow aspirate sample and the whole blood sample should be collected as they are **not** exploratory research biomarker samples. Both of these samples for MRD analysis are part of the response assessments in the main study; therefore, these samples are a required part of the study and **should always be collected**. Following MRD analysis on the whole blood sample, any remaining sample will be discarded rather than being used for molecular profiling.

CCI [REDACTED]

[REDACTED]

[REDACTED]

[REDACTED]

[REDACTED]

CCI

[REDACTED]

[REDACTED]

[REDACTED]

CCI

[REDACTED]

[REDACTED]

[REDACTED]

[REDACTED]

[REDACTED]

CCI [REDACTED]

[REDACTED]

[REDACTED]

[REDACTED]

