### **Disease specific efficacy endpoints**

CR, CRMRD-neg (a subgroup of CR), CRi, Morphological Leukemia Free State, and Partial Remission, as defined according to the 2017 ELN recommendations, and CR with partial hematologic recovery (CRh) for the Non-intensive study only. Note that CR (including CRMRD-neg) is a deeper response than CRh, and CRh is a deeper response than CRi. CR (including CRMRD-neg) is always a deeper response than CRi.

Note that patients whose MRD status cannot be determined (eg, due to lack of proper identification of a baseline immunophenotype from aspirate or peripheral blood) will not be allowed to resume single-agent therapy post HSCT or post consolidation. An MRD status will not be determined and the best response possible will be CR with no MRD status associated with the response.

Following Consolidation or following HSCT, the MRD result must be confirmed by 2 consecutive central laboratory results. Once confirmed, this will be used as the MRD result.

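### As printed, Appendix 4 leaves an MRD-negative remission with incomplete blood counts in no remission class, and no visible SAP rule settles the case

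*Protocol*

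**What the plan says.** The MRD column of Protocol Appendix 4 reads "MRD positive or unknown" in the rows for CR, CRh, CRi, MLFS and PR. For CR this makes sense, because a separate row takes the MRD-negative patients. That row requires neutrophils ≥1 and platelets ≥100 × 10⁹/L. CRh, CRi and MLFS have no MRD-negative counterpart. Footnote 1 calls the table a modification of the 2017 ELN criteria and adds: "The definitions used in this study are shown in this table".

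Two fallback classes catch whatever is left. Stable disease is "Absence of CRMRD-, CR, CRh (if applicable), CRi, PR, MLFS, and criteria for PD not met", with a three-month minimum in the non-intensive study. Protocol 7.2.1 lists the central MRD result among the response inputs and says that "response should be marked as indeterminate if the evaluation does not meet a specific ELN response criterion". Protocol 7.2.3 makes MRD sampling compulsory: "Both of these samples for MRD analysis are part of the response assessments in the main study".

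Other places treat MRD differently. Protocol 7.2.1 describes CRh by counts alone, "without qualifying for CR", with no MRD condition. Protocol 9.3.2 and SAP 3.2.1 use MRD only to mark a subset of CR; SAP 3.2.1 lists the MRD-negative class as "a subgroup of CR), CRi, Morphological Leukemia Free State, and Partial Remission, as defined according to the 2017 ELN recommendations". SAP Section 3 says that the investigator assesses response on local data and that a central laboratory determines MRD.

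**The concern.** On the literal table a better MRD result gives a worse response class. A patient who is CRi or CRh with positive or unknown MRD drops out of remission altogether if the central report comes back negative before counts recover.

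The endpoints that depend on these classes are:

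- CRi or better (both studies) and CRh or better (non-intensive), which SAP 6.2.2 compares between arms with a stratified CMH test.
- Duration of response. The patient either leaves the responder set or, if full CR follows, starts the clock later.
- Time to response in the non-intensive study, for the same reason.
- Non-intensive EFS under the visible definition. A patient with CRh-level counts who does not otherwise reach CR within six cycles becomes a treatment failure dated to randomization.

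OS, its boundaries, the OS-then-Fatigue hierarchy and the visible intensive EFS failure definition, which rests on CR alone, do not use these rows.

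**Working it through.** The plan states no figure to reproduce, because this is a classification rule. The check applies each Appendix 4 row to constructed cases and then looks for text that would change the result.

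**Step 1, the rows.** All cases have 0% peripheral blasts, under 5% marrow blasts, no extramedullary disease and no Auer rods. The count rules follow the last column of the table: CRh needs neutrophils ≥0.5 and platelets ≥50 without full recovery. CRi needs either count below 1 or 100 (intensive), or below 0.5 or 50 (non-intensive). The table gives the highest class met.

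| Neutrophils / platelets (× 10⁹/L) | Intensive, MRD positive or unknown | Intensive, MRD negative | Non-intensive, MRD positive or unknown | Non-intensive, MRD negative |
|---|---|---|---|---|
| 1.2 / 120 | CR | CR, MRD-negative | CR | CR, MRD-negative |
| 0.7 / 120 | CRi | none | CRh | none |
| 0.7 / 70 | CRi | none | CRh | none |
| 1.2 / 70 | CRi | none | CRh | none |
| 0.3 / 120 | CRi | none | CRi | none |
| 1.2 / 30 | CRi | none | CRi | none |
| 0.3 / 30 | CRi | none | CRi | none |

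With a negative MRD result, all six incomplete-count combinations in each study meet no remission class. MLFS does not catch them, because its row has the same MRD condition. PR does not either, because it needs 5–25% marrow blasts. These are constructed cases, not patient counts.

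**Step 2, text that might correct it.**

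- The counts-only CRh of Protocol 7.2.1 recovers the three non-intensive CRh cases. The three non-intensive CRi cases and all six intensive cases stay unclassified.
- SAP 3.2.1 covers MRD that cannot be determined, and confirmation by two consecutive results after consolidation or HSCT. Neither is this case.
- SAP 5.2.5 fixes the date of a response, not its class.
- SAP 6.2.2 sorts indeterminate responses by reason. No reason concerns MRD, and nothing there reclassifies them.

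**Step 3, the rows without the MRD condition.** Every case is then classified: CRi in six of six (intensive), CRh in three and CRi in three (non-intensive).

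**Step 4, EFS.** In the non-intensive study the three CRh-level cases change from non-failure to failure unless CR is reached within six cycles. The three CRi-level cases are failures either way, because the visible definition requires CRh or better.

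**Step 5, size per patient.** With 1:1 randomization the arms have 400/2 = 200 and 320/2 = 160 patients. One reclassified patient moves an arm's rate by 1/200 = 0.5 points or 1/160 = 0.625, about 0.6 points.

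**The case against.** **The cell is loose drafting.** The last column explains CRi by counts alone after the words "Not qualifying for CR or CRh (if applicable", and it overrides the printed count cells in the same row. It would be selective to follow that column for counts and hold the MRD cell absolute. This has force, and a slip is the likeliest explanation. But the last column expressly replaces the count cells and says nothing about MRD, so the printed condition remains.

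**MRD will usually be unknown when response is recorded.** SAP Section 3 separates local response assessment from central MRD. If the form is completed before the central report arrives, CRi and CRh apply as printed. This stands, and it is the main reason to expect a small practical effect. It is not a written rule: Protocol 7.2.1 lists MRD among the response inputs, so the class could depend on when a report arrives.

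**The SAP points to ELN 2017, and Protocol Section 9 lets the SAP modify the protocol.** If the published criteria set no MRD limit, the analysis definition might not carry one. That source cannot be checked here, and footnote 1 says that the study modifies it. The pointer leaves the question open.

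**A stronger reading.** A reader might infer a number of lost responders. For example, the 8% rate of remission without count recovery in Protocol 1.3.2, applied to 400 patients, gives 0.08 × 400 = 32. The documents do not support that. The figure comes from another trial, which also enrolled high-risk MDS, and the sum assumes that every such patient is MRD-negative. No MRD-negative share is given anywhere.

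**Conclusion.** The definition is wrong as written, and the point is minor. Appendix 4 governs, its MRD column excludes MRD-negative patients with incomplete counts from every remission class, and the visible SAP does not resolve the case. It conflicts directly with Protocol 7.2.1 for CRh only, since that section does not define CRi or MLFS. Protocol 9.3.2 and SAP 3.2.1 state no opposing rule; the table simply does not fit the role they give MRD.

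The number of affected patients cannot be derived from the documents and is probably small. Each one moves an arm's rate by 0.5 or 0.6 points. Nothing shows that the arms would be affected differently, so a reader should not infer bias in the comparison. Nor does the point reach the primary result: the affected endpoints lie outside the OS-then-Fatigue sequence.

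The conclusion rests on the literal reading of the table and on the unredacted SAP text. SAP 6.2.5 refers to several EFS definitions, and the effect on the redacted ones is unknown.

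**What to change.** 1. For the analysis of response endpoints, correct Appendix 4 and state in SAP 3.2.1 that CRh, CRi and MLFS apply whatever the MRD status, and that MRD only splits CR. SAP 3.2.1 should cite Appendix 4 as corrected.
2. Reconcile or explain the same MRD wording in the PR row.
3. Before unblinding, query with the investigator any assessment recorded as stable disease or indeterminate with under 5% marrow blasts and a central MRD-negative result. A query keeps the endpoint investigator-assessed; programmed re-derivation would not.
4. Align the CRh thresholds, which are strict (>0.5 and >50) in Protocol 7.2.1 and inclusive (≥0.5 and ≥50) in Appendix 4.
5. Appendix 4 also builds Treatment Failure on CR, CRi and CRh, and Protocol 6.5 lists Treatment Failure as a reason for withdrawing study treatment in the intensive study. Those passages must be reconciled with the corrected table. No clinical rule is proposed here.

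The cost is a few table cells, one threshold alignment, a short SAP statement and a limited blinded query round, with no new data collection. The table change is a protocol amendment and needs the IRB/EC approval described in Protocol 12.1.
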